4.2 Re-invitation intervals

On October 17, 2016, the re-invitation interval for those in arm 1+2 with PSA 2.4-2.99 was changed from 1 to 2 years. Men already informed that they would be re-invited after one year were notified that the invitation would be postponed one year.

Re-invitation interval algorithm:

Re-invitation intervals	
Arms 1+2 + 3	
PSA (ng/mL)	Interval (years)
≤0.59	8
0.6 – 1.19	4
≥ 1.2	2

Special re-invitation intervals	
Subjects	Interval (years)
Non-participation in any round	2*
Negative biopsy and/or negative MRI twice in a row	4
PSA ≥3, neither MRI nor biopsy performed	2
PSA ≥3, positive MRI, no biopsies performed	2

Men not participating at invitation in round 1 will receive a reminder after 3 and 9 months. In subsequent round no reminders will be sent out.

4.3 Upper age limit

On October 1, 2015, the algorithm for upper age limit, defined at time of study start (updated with new PSA-thresholds 2020), was updated (see amendment 2).

The new algorithm:

Upper age limit (no more screening)	
All arms	
PSA (ng/mL)	Age (years)
≤ 0.59	≥62
0.6 – 1.19	≥65
1.2 – 1.79	≥70
≥ 1.8	≥75

4.4 Special circumstances

Due to high risk of potentially lethal prostate cancer, all men with PSA ≥ 10.0 ng/mL, irrespective of Study Arm, will, for ethical reasons, be recommended 12 standard TRUS-biopsies plus additional targeted biopsies if positive MRI. Exceptions are those with PSAD < 0.1.

On March 1, 2016, the PSA level indicating high risk of lethal prostate cancer was adjusted from ≥ 20.0 ng/mL to PSA ≥ 10.0 ng/mL in order to harmonize with National standardized course of medical care (SVF) for prostate cancer.

Since October 15, 2018, all men with MRI showing a PI-RADS-score 5 in Arm 2 and Arm 3, should, apart from the targeted biopsies, also undergo systematic biopsies with 12 cores. All men with PI-RADS 5 lesions and negative biopsies should be re-evaluated at a radiology conference (round) and, if no adjustment of PI-RADS score, a new set of targeted biopsies should be carried out within 3 months.

The study design is depicted in Figure 1.

5 Study organisation and infrastructure

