4 STUDY INTERVENTION

4.1 Intervention

Arm (1) (reference arm)

- Screen-negative: If the total-PSA level is “normal”, i.e. below the cut-off 3.0 ng/mL, no further testing or examination will be performed, but all men will be re-invited.
- Screen-positive: If the total-PSA level is “elevated” above the cut-off i.e. ≥ 3.0 ng/mL, the man will be invited for an MRI.

All men will be recommended standard biopsy, i.e., digital rectal exam followed by TRUS-guided 12-core standard prostate biopsy according to the screening protocol. These standard biopsies will be taken with both the urologist and subject blinded to the MRI result. After these standard biopsies, the study nurse will show the urologist the result from the MRI examination, and in case of suspicious lesion at MRI, 3-4 targeted* biopsies in each of these lesions will be performed in the same séance; 3 targeted biopsies if one of the systematic biopsies already hit the area, and 4 targeted biopsies if otherwise.

- Men in whom MRI for any reason is not achievable or the result is inconclusive will only undergo systematic biopsies

Arm (2) (first experimental arm)

- Screen-negative: If the total-PSA level is “normal”, i.e., below 3.0 ng/mL, no further testing or examination will be performed. The man will be re-invited for screening identical to Arm (1).
- Screen-positive: If the total-PSA level is “elevated” ≥ 3.0 ng/mL, he will be offered MRI.
 - If the MRI is positive (PI-RADS 3-4), only targeted* biopsies will be performed, i.e. 4 biopsy cores targeted against each suspicious lesion, but no systematic biopsies.
 - If the MRI is positive (PI-RADS 5), targeted* biopsies will be performed, i.e., 4 biopsy cores targeted against each suspicious lesion but also systematic biopsies. Changed 2018-10-15 (see amendment 5)
 - If the MRI is negative no biopsies will be performed.
 - If the MRI is negative and PSA ≥ 10 and PSA density (PSAD), ≥ 0.1 , systematic 12-core biopsies will be performed. PSA cut off changed 2016-03-01 from 20 to 10 ng/mL (see amendment 1).
 - Men in whom MRI for any reason is not achievable, or the MRI is technically inferior (for example in men with hip prosthesis), are invited for urological examination with digital rectal examination (DRE) and transrectal ultrasound

(TRUS). These men are included in the intention to screen analysis but not in the per protocol analysis (see 6.2.1).

Arm (3) (experimental arm II)

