6 STATISTICAL CONSIDERATIONS

6.1 Sample Size Calculation

The hypothesis is that the MRI-targeted biopsy only strategy would reduce insignificant cancer with 50%. Based on previous studies and expert knowledge, we assumed that the proportion of men diagnosed with insignificant cancer among men with PSA ≥ 3 in Arm 1 (reference arm) would be 9%. This gave a sample size of N=1,164 men with PSA ≥ 3 ng/mL to achieve 80% power, when having a two-sided test alternative and significance level 5%. Furthermore, we hypothesized that 7% among men attending PSA-screening would have an elevated PSA and that the participation rate would be 50%, which lead to the sample size N=33,260 altogether in the three screening-arms. Accounting for uncertainty in the hypothesized proportion of insignificant cancers and in the proportion of men with PSA ≥ 3

ng/mL among those screened, lead to the final sample size of N=36,000 for the SG. With an allocation rate of 1:2 between the CG and SG, altogether, N=54,000 men are needed to be included in the study.

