6.2 Analysis plan for the primary and secondary endpoints

6.2.1 Primary objective (Detection of insignificant cancer)

- Hypothesis

The proportion of men with insignificant cancer detected by PSA testing with threshold 3 ng/mL, systematic biopsies and MRI-targeted biopsies (p_1) will be different from the proportion detected when omitting systematic biopsies (p_2):

H_0 (null hypothesis): $p_1 = p_2$

H_A (alternative hypothesis): $p_1 \neq p_2$

Although the hypothesis of the investigators is one-sided, that MRI-targeted biopsies only will lower the proportion, the test is two-sided to allow for a significant effect in both directions.

- Analysis populations

First assessment (after completion of screening round 1): All men in arm 1 will be compared to all men in arm 2 and 3 combined. However, for men in arm 3, cancers detected in men with PSA < 3 ng/mL will be ignored.

Later assessments: the analysis will compare all men in arm 1 with all men in arm 2.

The analyses will primarily be carried out according to the intention to treat (ITT) principle, which here means that all men will be included in the analysis and belong to the arm they were allocated to, irrespective of whether they completed the intended diagnostic pathway with MRI and biopsies or not.

Furthermore, per protocol analyses will be carried out including only men who strictly follow the protocol.

An additional analyses will compare men in arm 1 who underwent MRI followed by systematic and possible targeted biopsies (if MRI positive) with those in arm 2 and 3 who underwent MRI and also targeted biopsies but ignoring results from possible systematic biopsies if those were taken at the primary biopsy and the targeted biopsies were benign.

- Analysis

Outcome measure is the relative difference of the proportion of insignificant cancers detected in arms 2 and 3 combined vs arm 1 (the cancers detected in men with PSA below 3 ng/mL in arm 3 will be ignored). In later assessments only arm 1 and 2 will be included. The result will be presented as a point estimate with a two-sided 95% confidence interval, and a p-value of the hypothesis test. Significance testing will only be carried out for the first definition of insignificant cancer (Gleason grade 3+3). The score method will be used for testing and confidence intervals (27). A p-value below 5% will be considered statistically significant.

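### Section 4.1 conflicts with 4.4 and 5.1 on systematic cores for some men with PSA ≥ 10 in arms 2/3, and such cores count in a proportion described as omitting them

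*Protocol*

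**What the plan says.** Protocol section 6.2.1 sets up the primary hypothesis as follows: the proportion with insignificant cancer under PSA testing, systematic and targeted biopsies (p1) "will be different from the proportion detected when omitting systematic biopsies" (p2). At the first assessment p2 comes from arms 2 and 3 combined. Section 6.2.2 analyses significant cancer in the same way but without a test.

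Three places say which biopsies men in arms 2 and 3 receive.

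- Section 4.1, for PI-RADS 3–4: "only targeted* biopsies will be performed, i.e. 4 biopsy cores targeted against each suspicious lesion, but no systematic biopsies". Its only exception for high PSA concerns a negative MRI with PSA ≥ 10 and PSAD ≥ 0.1, where 12 systematic cores are taken. Arm 3 follows arm 2 apart from the PSA cut-off.
- Section 4.4: men with PSA ≥ 10 ng/mL, "irrespective of Study Arm, will, for ethical reasons, be recommended 12 standard TRUS-biopsies plus additional targeted biopsies if positive MRI", with an exception for PSAD below 0.1.
- Section 5.1 states which biopsy sets are used for the endpoints. Its table has separate columns for arms 2 and 3 with PSA ≥ 10 and PSAD ≥ 0.1: systematic plus targeted cores if MRI is positive, 12 systematic cores if it is negative.

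The end of section 4.1 adds that, in round 1, men in arms 2 and 3 with cancer on targeted cores are recommended later systematic cores, at any PSA.

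**The concern.** There are two linked problems. First, a man in arm 2 or 3 with PSA ≥ 10, PSAD ≥ 0.1 and a PI-RADS 3–4 lesion has two incompatible biopsy instructions in one protocol. Second, under sections 4.4 and 5.1 the men in this PSA/PSAD stratum of arms 2 and 3 receive essentially the arm 1 biopsy set, yet they contribute to a proportion described as the yield without systematic biopsies.

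A stratum handled alike in all arms carries almost no contrast, so the overall ratio moves toward 1. For insignificant cancer, where a reduction is expected, that costs power. For significant cancer, the section 2.2 objective is that detection is kept up, so a ratio nearer 1 is the welcome answer. Section 4.4 itself gives the high risk of lethal cancer in these men as its reason for the rule, so they may well hold a larger share of significant than of insignificant cancers. A reader could then credit targeted-only biopsy with keeping detection in men who were not managed by it.

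**Working it through.** **1. The passages side by side, arms 2 and 3, PSA ≥ 10**

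| Man | 4.1 | 4.4 | 5.1 table |
|---|---|---|---|
| PSAD ≥ 0.1, PI-RADS 3–4 | targeted only | systematic + targeted | systematic + targeted |
| PSAD ≥ 0.1, MRI negative | 12 systematic | 12 systematic | 12 systematic |
| PSAD < 0.1, PI-RADS 3–4 | targeted only | excepted | targeted; 12 later if cancer |
| PSAD < 0.1, MRI negative | none | excepted | none |

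Only the first row conflicts. Because men with cancer on targeted cores are recommended systematic cores later in round 1 anyway, that conflict changes whether cancer is found only when the targeted cores are benign.

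**2. Does a planned analysis in 6.2.1 remove these cores?**

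- Intention to treat keeps them.
- Per protocol keeps them, since they follow the protocol.
- The additional analysis ignores systematic cores taken at the primary biopsy when targeted cores were benign. That covers MRI-positive men. It takes arm 2/3 men who had MRI and targeted cores, so it states no rule for MRI-negative men biopsied because of high PSA.

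**3. The plan's own sample size**

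Inputs from section 6.1: p1 = 0.09, a 50% reduction giving p2 = 0.045, two-sided 5%, power 80%. From section 3.5, 1:1:1 allocation makes arm 1 vs arms 2+3 a 1:2 split (k = 2). With p̄ = (0.09 + 2 × 0.045)/3 = 0.06:

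n1 = [1.96·√((1 + 1/k)·p̄(1 − p̄)) + 0.84·√(p1(1 − p1) + p2(1 − p2)/k)]² / (p1 − p2)²

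This gives 350 + 700 = 1,050. With continuity correction it gives 382 + 764 = 1,146, which is 1.5% below the stated figure ("This gave a sample size of N=1,164 men with PSA ≥ 3 ng/mL"). Also 1,164/0.07/0.50 = 33,257, against 33,260 stated. The figure is reproduced closely enough.

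**4. Insignificant cancer**

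Let f be the share of arm 1 insignificant cancers in the PSA ≥ 10, PSAD ≥ 0.1 stratum. Assume equal detection across arms inside it and a ratio of 0.50 outside it:

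RR = f + (1 − f) × 0.50, and p2 = 0.09 × RR.

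Power is at 388 vs 776 men (1,164 in all), pooled, without continuity correction.

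| f (assumed) | RR | Power |
|---|---|---|
| 0 | 0.50 | 83.7% |
| 3% | 0.515 | 81.2% |
| 5% | 0.525 | 79.4% |
| 10% | 0.55 | 74.6% |
| 15% | 0.575 | 69.2% |
| 20% | 0.60 | 63.5% |

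At the 1,260 men implied by the final size (36,000 × 0.50 × 0.07), power is 82.3% at f = 5% and 77.6% at f = 10%. If the planned 50% was already meant for the strategy with its high-PSA rule, there is no loss against plan.

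**5. Significant cancer**

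Let s be the stratum's share of arm 1 significant cancers and r the ratio elsewhere. The observed ratio is s + (1 − s)·r.

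| r | s = 5% | 10% | 20% | 30% |
|---|---|---|---|---|
| 0.70 | 0.715 | 0.73 | 0.76 | 0.79 |
| 0.80 | 0.81 | 0.82 | 0.84 | 0.86 |
| 0.90 | 0.905 | 0.91 | 0.92 | 0.93 |

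Since 1 − [s + (1 − s)r] = (1 − s)(1 − r), the fraction of the loss that is masked equals s. The table therefore shows direction and scale; it is not evidence about s.

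**6. Can the stratum be set aside without breaking randomisation?**

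Under section 3.5, arm allocation is triggered by the first PSA result reaching the database. Allocation PSA is thus fixed before the arm, and restricting all arms to 3.0–9.99 compares randomised groups. PSAD is not known at that moment, so it should not define the set. The restriction also removes men with PSA 10–19.99, for whom the rule changed on 1 March 2016, when the threshold moved from 20 to 10.

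**The case against.** The high-PSA rule is disclosed in 4.1, 4.4 and 5.1, and section 8.3 describes omission of biopsy as applying to negative MRI with PSA below 10. Intention to treat compares the strategies as offered, which is a legitimate contrast. This stands: the fault lies in how p2 is described, not in the comparison.

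Section 4.4 is headed as special circumstances and 5.1 defines the endpoint set, so 4.1 may only lack a cross-reference. That may be so, but 4.1 as written excludes systematic cores for PI-RADS 3–4 and names a PSA exception for negative MRI alone.

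Section 3 lists a within-arm-1 comparison that is free of this problem and includes men with PSA ≥ 10. It is useful and should be cited alongside. It does not alter what p2 measures in the randomised comparison.

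Three stronger readings are tempting but not supported:

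- **A second contradiction, for arm 1 with PSAD < 0.1.** Section 4.1 says of arm 1 that "All men will be recommended standard biopsy", and the 4.4 exception might seem to release such a man. The natural reading is that the exception lifts only the special rule and returns him to his arm's ordinary pathway. The arm 1 columns in 5.1 agree.
- **An inflated error rate for significant cancer.** Section 6.2.2 has no test and the protocol states no margin, so only the interpretation of an estimate is affected.
- **The main conclusion should move to the PSA 3.0–9.99 set.** That would replace the full randomised population. It would drop men with PSA ≥ 10 and PSAD < 0.1 who do follow targeted-only biopsy. It also fits only round 1: later assessments span several rounds, and men whose first PSA was below 3 would be lost.

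**Conclusion.** The point holds in a limited form. Section 4.1 contradicts 4.4 and the 5.1 table for arm 2/3 men with PSA ≥ 10, PSAD ≥ 0.1 and PI-RADS 3–4. Separately, systematic cores in arm 2/3 men with PSA ≥ 10 and PSAD ≥ 0.1 count toward a proportion worded as omitting them.

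The intention-to-treat result answers a question about the strategy with its PSA/PSAD rule. As an answer about targeted-only biopsy it is shifted toward no difference: conservative for the primary endpoint, favourable for the untested estimate of significant cancer. The protocol gives no stratum shares, so the size is unknown. The figures above rest on assumed shares, equal detection within the stratum, and (for the power figures) the planned 50% applying only outside it. They show a small effect for shares of a few per cent and a material one at 20–30%.

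**What to change.** 1. Reconcile section 4.1 with section 4.4 and the 5.1 table for arm 2/3 men with PSA ≥ 10, PSAD ≥ 0.1 and PI-RADS 3–4. Which rule should apply is for the investigators.
2. Reword p2 in 6.2.1, and the conclusion drawn from it, as detection under the MRI-targeted strategy including its PSA/PSAD rule. Keep intention to treat as the primary analysis.
3. For the round 1 assessment, add a supportive comparison of arms 2+3 with arm 1, restricted in all arms to allocation PSA 3.0–9.99 ng/mL, for insignificant and significant cancer. Qualify by it any statement about omitting systematic biopsies or keeping up detection.

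The cost is some wording and one extra analysis on data already held, with a slightly wider interval from the smaller set. The restricted set removes the high-PSA rule only. Later systematic cores after a positive targeted biopsy remain in it, as do any systematic cores added for PI-RADS 5, and the report should say so.

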5.1 Outcome Ascertainment

The project is planned to run for an initial 4 years with an evaluation of the primary and some of the secondary objectives during year 4. Details of outcomes and times of assessments are given in Table 1 (p 19)

Prostate cancer diagnosis

Reporting of cancer to the National Prostate Cancer Register and the National Cancer Register is mandatory by Swedish law. All diagnoses made in the study will be continuously recorded in the study database. Every 3 months, cross-linkage on the study participants' personal identification number will also be performed with the study database and the cancer registries, to ensure accuracy and completeness of the diagnoses.

Prostate biopsies

One internal pathologist with 25 years of experience of prostate pathology will review the prostate biopsies in the study. To minimize heterogeneity in Gleason grading between different pathologists a secondary review of biopsies with a cancer diagnosis will be conducted by two external pathologists. The reviewers are blinded to the primary local assessment and work independently from each other. Each core harbouring cancer is reviewed separately. The final Gleason score for each patient is based upon these three verdicts. In case of agreement between at least two of the reviewers the Gleason score is set. In case all three reviewers differ from each other the "middle" assessment will be used. In the first screening round the internal pathologist is [name] with 25 years of experience of prostate pathology, and the external pathologists are [name] at Karolinska Institute, Stockholm and [name] at University of Oslo.

Reference for biopsy outcome

For analysing the endpoints based on prostate biopsies, different sets of biopsies will be taken into account (see table below). Adding systematic biopsies at a second occasion in men with cancer detected with targeted biopsies in arms 2 and 3 is an attempt to compensate for possible sampling errors due to the fact that MR positive and MR negative cancers were primarily biopsied with two different techniques. Only systematic biopsies taken within one year after the diagnostic biopsy are taken into account (arms 2 and 3).

If MRI, for any reason, is not achievable or inconclusive, see 4.1

Additional biopsies taken after what here is stated are not considered

Arm 1	Arm, 1	Arm 2 and 3 (PSA < 10 ng/mL or PSA ≥ 10 and PSAD < 0.1)		Arm 2 and 3 (PSA ≥10 ng/mL and PSAD ≥0.1)	
MRI pos*	MRI neg	MRI pos **, ***	MRI neg	MRI pos*	MRI neg
12 systematic plus 3-4 targeted biopsies	12 systematic biopsies	4 targeted biopsies. If cancer. 12 additional cores at a later occasion	No biopsies	12 systematic plus 3-4 targeted* biopsies	12 systematic biopsies

- * If the MRI positive sector is sampled with one core in the systematic biopsies, 3 extra targeted biopsies are sampled from that sector, otherwise 4 biopsies
- ** If MRI shows PI-RADS 5, 12 systematic biopsies are added (not in screening round 1)
- ***If cancer is found in the targeted biopsies patients are rescheduled for systematic biopsies

Prostatectomy specimen

Prostatectomy specimen will be processed according to Swedish standard (KVA document) and reviewed at the department of Pathology at Sahlgrenska University Hospital. Tumor volume will be assessed by the planimetric method. Endpoint definitions for prostatectomy specimen are given in table 3, p

Prostate cancer mortality

The project is planned to continue to allow evaluating long-term effects on prostate cancer mortality. In the Göteborg-1 trial [9], an independent Cause of death (COD) committee consisting of 3 urology professors, blinded to study allocation, reviewed the cause of death following a standardized algorithm. A similar COD committee will be used in this study.

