Biopsy of the prostate will be carried out by a limited number of urologists (n=5), with several years of prostate biopsy experience (5-30 years), using existing equipment at the Dept. of Urology, Sahlgrenska University Hospital. Biopsies are conducted by a B&K equipment and directed by transrectal ultrasound (TRUS) guidance. Fusion biopsies will be used in selected cases but cognitive directed biopsies will be the standard.

On December 14, 2016, the number of cores in systematic biopsies was increased from 10 to 12 cores (see Amendment 9). All 12 cores are directed against the posterior aspect of the prostate. We use the same sector-system as in the National Swedish Prostate Cancer Registry (NPCR) which comprises 12 posterior and 12 anterior sectors. In case of a positive MRI finding in one of the sectors included in the systematic biopsies among men in Arm 1, one of the targeted cores from that sector is appointed as belonging to the “systematic biopsies” and the remaining three cores as targeted. In case of a MRI lesion in a sector not included in the systematic biopsies all 4 cores are designated as targeted.

The MRIs of men with PI-RADS 5 and a negative biopsy will, since January 16, 2020, be demonstrated at a prostate MRI radiology conference and these men will be re-invited after 3 months for a repeated targeted biopsy.

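### Protocol 5.1 does not count the repeat targeted biopsy that 4.4 and 5.2 ask for after a negative PI-RADS 5 biopsy, so a cancer first found there is scored as no cancer

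*Protocol*

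**What the plan says.** **The work-up.** Protocol 4.4 sends men with a PI-RADS 5 lesion and negative biopsies to a radiology conference, and then: "if no adjustment of PI-RADS score, a new set of targeted biopsies should be carried out within 3 months". Protocol 5.2 describes the same step, in force since January 16, 2020, as: "these men will be re-invited after 3 months for a repeated targeted biopsy". Neither section limits it to particular arms.

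**The counting rule.** Protocol 5.1 opens its reference for biopsy outcome with "For analysing the endpoints based on prostate biopsies, different sets of biopsies will be taken into account (see table below". For MRI-positive men in arms 2 and 3, outside the group with PSA ≥ 10 and PSA density ≥ 0.1, the table entry is "4 targeted biopsies. If cancer. 12 additional cores at a later occasion". A footnote to that entry reads "If MRI shows PI-RADS 5, 12 systematic biopsies are added (not in screening round 1". On later sessions, 5.1 says "Only systematic biopsies taken within one year after the diagnostic biopsy are taken into account (arms 2 and 3". It closes the list with "Additional biopsies taken after what here is stated are not considered".

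**The analysis set.** Under 6.2.1 the main analysis is by intention to treat: each man stays in his allocated arm whether or not he completed the diagnostic pathway.

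**The concern.** The repeat biopsy belongs to the trial's own algorithm, but the endpoint is defined without it. A man whose PI-RADS 5 lesion is missed at the first session and found to hold cancer at the repeat stays in the denominator and adds nothing to the numerator for that visit.

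The secondary objective asks whether MRI-targeted biopsy maintains detection of significant cancer. It would be assessed without some of the cancers that the algorithm under test finds. The count of insignificant cancers, which carries the primary test, is also affected, though less under the assumptions used here. Section 5.1 does not treat second sessions alike: one that follows a positive first biopsy in arms 2 and 3 counts, while one that the protocol requests after a negative first biopsy does not.

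**Working it through.** **1. Does any listed set contain the repeat?**

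| Biopsy | Asked for in | Counted by 5.1? |
|---|---|---|
| First-session systematic and targeted cores | 4.1 | Yes, in the table |
| Systematic cores added for PI-RADS 5, arms 2/3 | 4.1, 4.4 | Yes, by footnote, but not in round 1 |
| Completion systematic cores after a positive targeted biopsy, arms 2/3 | 4.1 | Yes, within one year |
| Repeat targeted biopsy after a negative PI-RADS 5 biopsy | 4.4, 5.2 | No; caught by the closing exclusion |

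No other section brings the repeat back. The registry linkage in 5.1 records such a cancer but does not override the counting rule.

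**2. Which assessments are exposed?** October 15, 2018 (4.4) is the date of the added systematic cores. The only start date for the repeat is January 16, 2020 (5.2). Section 9.3.1 places the completion of round 1 in 2021. The repeat therefore touches the last part of round 1 and, from 2020 on, the visits of later rounds, which enter the assessments from June 30, 2022 onward (2.5). The re-invitation table in 4.2 has no three-month entry, so it is not stated which visit would own the cancer.

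**3. Do the arms differ?** In later rounds the footnote gives PI-RADS 5 men in arms 2 and 3 systematic plus targeted cores, close to arm 1. The lesion itself is sampled similarly throughout: 4 targeted cores, or 3 plus a systematic core already in that area. A difference in first-session sampling remains only between January 2020 and the end of round 1, and only if the footnote's round-1 exception prevails over 4.1 and 4.4, which date the change to October 2018 without limiting it by round.

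**4. Size.** The documents give no PI-RADS 5 frequency, no first-biopsy negative rate and no repeat yield. The protocol's planning figures do not depend on this point and reproduce: at 9% against 4.5%, allocation 1:2, two-sided 5%, 80% power and a continuity correction, I obtain 382 men in arm 1 and 1,146 in total, 1.5% below the stated 1,164. Then 1,164 / (0.07 × 0.50) = 33,257, against the stated 33,260.

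Assumptions (not from the documents): 3–10% of men with PSA ≥ 3 have PI-RADS 5; 10–30% of these are negative at the first biopsy; 30–60% of repeats find cancer; 20–40% of those cancers are Gleason 6. Per 1,000 men with PSA ≥ 3 to whom the repeat applies:

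- Uncounted cancers: 1,000 × 0.03 × 0.10 × 0.30 = 0.9, up to 1,000 × 0.10 × 0.30 × 0.60 = 18.
- Of these, Gleason 6: 0.9 × 0.20 = 0.18, up to 18 × 0.40 = 7.2.
- Of these, above Gleason 6: 0.9 × 0.60 = 0.54, up to 18 × 0.80 = 14.4.

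Effect on the planned ratio for insignificant cancer (45 / 90 = 0.50 per 1,000):

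- Counted equally in all arms: (45 + 0.18) / (90 + 0.18) = 0.501, up to (45 + 7.2) / (90 + 7.2) = 0.537.
- If they arose only in arms 2 and 3: 45.18 / 90 = 0.502, up to 52.2 / 90 = 0.580. Step 3 makes this an extreme case.

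With 388 against 776 men (1,164 split 1:2, no continuity correction), power is 0.84 as planned and 0.80–0.84 with the repeats counted in all arms. No planning rate is given for significant cancer, so no ratio can be computed there.

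**The case against.** The strongest defence is that 5.1 makes an explicit choice: the endpoint is what the first work-up finds, the list is closed, and the same rule binds every arm. A repeat introduced in January 2020 would have round-1 men scored under two definitions depending on calendar date. The protocol protects round 1 elsewhere too, through the footnote and through the additional analysis in 6.2.1 that ignores systematic cores when targeted cores were benign. The secondary endpoint has no hypothesis test (6.2.2) and the effect on the primary ratio is small.

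The point about round 1 stands, and the fix allows for it. The general defence does not: 5.1 is not a first-session rule, since it admits second-occasion systematic cores for up to a year in arms 2 and 3. Its reason for doing so, possible sampling error, applies at least as well to a missed PI-RADS 5 lesion.

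Three stronger readings should be resisted.

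- *The rule biases the comparison against arms 2 and 3.* Step 3 of the working confines any imbalance to late round 1, and even there it depends on an unresolved conflict in the text.
- *Cancers in PI-RADS 5 men are lost in general.* Only those first found at the repeat are affected, and 4.4 makes the repeat conditional on the score being upheld.
- *Such a man can never be recovered in later assessments.* That he leaves screening once diagnosed is a reasonable inference, but no section says how he is handled.

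**Conclusion.** The inconsistency is real. Followed literally, 5.1 scores a cancer first found at the requested repeat biopsy as no cancer for the triggering visit, in any arm. This under-counts what the screening algorithm detects, mainly in the later cumulative assessments and in the last part of round 1.

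The number cannot be derived from the documents and is probably small. The range of 0.9 to 18 per 1,000 rests wholly on assumed inputs. A reader might turn it into a count per arm and round, but the 7% and 50% in 6.1 are planning figures, and re-invitation at 2, 4 or 8 years by PSA (4.2) means that later rounds contain different men. The primary conclusion is unlikely to turn on this. It matters more for significant cancer, where 60–80% of the uncounted cases would fall under the same assumptions. It should be corrected, but does not threaten the trial.

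**What to change.** - **Later assessments.** In 5.1, add the repeat targeted biopsy after a negative PI-RADS 5 biopsy to the counted sets, in all three arms, attributed to the screening visit that triggered it and within one stated window.
- **Round 1.** The repeat existed only at the end of this round, so report the result with and without it.
- **Sensitivity.** Show first-session-only results, and say whether the completion systematic cores in arms 2 and 3 are left out as well.
- **Text to reconcile.** The timing of the repeat differs between 4.4 (inside three months) and 5.2 (after three months). The October 2018 change for PI-RADS 5 in 4.1 and 4.4 conflicts with the round-1 exception in the 5.1 footnote. The sponsor must say which applies; this review takes no position on either.

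The cost is one row in the 5.1 table and a fresh outcome derivation for a few men, from biopsies that the protocol already calls for. The downside is that a second session enters the endpoint for those men, which the sensitivity analysis makes visible.
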